# Evaluation of Cellphone Based Otoscopy in Pediatric Patients Protocol

## 1. Important definitions

- **Trainee**= any resident physician, physician assistant student, medical student, or physician assistant who works in the Harriet Lane Clinic (Acute and/or Continuity Clinics) or Johns Hopkins Children's Center Pediatric Emergency Department.
- **Supervisor**= any attending physician, pediatric emergency medicine fellow, general pediatrics preceptor, nurse practitioner who works in the Harriet Lane Clinic (Acute and/or Continuity Clinics) or Johns Hopkins Children's Center Pediatric Emergency Department.
- **External Ear:** the anatomy of the ear that includes the external auditory meatus, ear canal, tragus, antitragus, and concha. This specifically does not include the lobule of the ear and the helix.
- **Direct Visualization:** the act of looking directly through a magnifying lens and seeing a non-digital image.
- **Indirect Visualization:** the act of looking at a screen attached to a magnifying lens and seeing a digital image.
- **Non-sensitive area anatomy:** Human anatomy that does not include the genitals or breasts.

## 2. Objectives

Aim 1: To establish whether a smartphone otoscope improves diagnostic accuracy of tympanic membrane (TM) pathology for trainees, compared to supervisor.

Aim 2: To determine whether smartphone otoscope improves diagnostic confidence of trainees, thereby reducing frequency of antibiotic prescriptions for AOM.

Aim 3: To determine whether there is a change in repeat exam rates by supervisors, comparing with/without Cellscope.

Aim 4: To determine whether trainees convert to traditional otoscope use during the weeks that Cellscope is available.

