## 3. Study Procedures

### a. Study design, including the sequence and timing of study procedures

This is a prospective, randomized, unblinded, controlled study in the Harriet Lane Clinic (HLC), the Johns Hopkins Children's Center pediatric primary care resident teaching practice and the Johns Hopkins Children's Center Pediatric Emergency Department (Peds ED). The HLC has clinics for acute care (e.g., sick visits) and continuity (e.g., well child and follow-up visits). We will purchase Cellsopes, iPhones, phone cases, and locking storage systems for each setting. There will be no direct collaboration between the study investigators and Cellscope related to this study. We will evaluate the above aims by block-randomizing in 2-week blocks: 1 week where the Cellscope will be available and 1 week where only traditional otoscopy will be available. Because residents rotate through the HLC and Peds ED in 2 and 4-week rotations, this will allow for the inclusion of the same trainees in each arm to act as their own control and ensure there is no use of the Cellscope during the traditional-only weeks. During Cellscope weeks, the traditional direct otoscopes will be available based on trainee/supervisor preference. During the traditional weeks, the Cellscope will not be available, thus the standard of care will not be changed during our study. iPhones will be secured with 6-digit numeric passcodes, in compliance with JHMI security standards. Recordings/images of external and middle ear structures will be obtained in a HIPAA compliant manner without collecting any PHI.

During Cellscope weeks, trainees and supervisors will be given access to the Cellscope and asked to use this tool for their otoscopic exams (research procedure). They will have full discretion of when an otoscopic examination is indicated, based on their existing practice and standard of care. We will then ask that the

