trainees and supervisors each fill out an index card survey to record the following outcomes: agreement between trainee and supervisor using the OMgrade scale (validated otitis media diagnostic tool), trainee confidence in exam, antibiotic prescription, need for conversion to traditional otoscopy, and whether a repeat exam was obtained. During the traditional weeks, the Cellsopes will be unavailable, locked in an enclosure, and traditional otoscopy (routine care) will be the only method available. The same index card survey will be completed by the trainees and supervisors. There will be no change to patient restraint, as described above.

b. Study duration and number of study visits required of research participants.

The study will last for between 9-12 months depending on the number of patients enrolled. Only one study visit is required per research participant. The same patient will be able to be included in the study multiple times if they present to the HLC or Peds ED on multiple occasions.

c. Blinding, including justification for blinding or not blinding the trial, if applicable.

This study will be unblinded. It is not possible to perform this study in a blinded manner given the obvious difference in the handheld hardware.

d. Justification of why participants will not receive routine care or will have current therapy stopped.

Standard of care is traditional direct otoscopy, as described above. We are using an equivalent method of otoscopy that allows the identical visualization of the external and middle ear structures. It will also be explicitly stated to providers that they can revert to traditional otoscopy if they feel that the Cellscope is not able to identify the needed structures.

e. Justification for inclusion of a placebo or non-treatment group.

N/A

f. Definition of treatment failure or participant removal criteria.

If any provider feels that the Cellscope is not able to appropriately identify the needed ear structures, that will be considered a failure of the Cellscope, and that provider will be able to immediately revert to a traditional otoscope. Furthermore, patients and guardians may opt for providers to use the traditional otoscope at any time. This will be tracked.

g. Description of what happens to participants receiving therapy when study ends or if a participant's participation in the study ends prematurely.

Resumption of traditional care, without any harm to the patient.

h. Informed Consent

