**5. Study Statistics**

a. Primary outcome variable.

Aim 1:

- A. Inter-rater reliability between trainee and supervisor utilizing the OMgrade scale

Aim 2:

- A. Rates of patients who receive antibiotics

- B. Levels of provider confidence in exam based on a standardized confidence measure

Aim 3: Rate of repeat exams by supervisors with and without Cellscope

b. Secondary outcome variables.

Aim 4: Rate of provider decided use of traditional otoscopy during Cellscope weeks

c. Statistical plan including sample size justification and interim data analysis.

Descriptive statistics will be performed to analyze our outcome measures in conjunction with Johns Hopkins BEAD Core statisticians.

1. Calculation of descriptive statistics such as mean, median, SD, range will be employed.
2. Examination of graphs such as outcome vs. time, scatterplots of two variables, Kaplan-Meier curves.
3. Estimation of differences between two groups with comparison by t-test or Mann-Whitney test.
4. Estimation and testing of within-person changes by matched t-test or Wilcoxon signed-rank test.
5. Multiple linear regression, logistic regression, or Cox proportional hazards regression.
6. Repeated measures models (usually requires the help of a statistician).
7. Comparison of proportions by the determination of kappa values will be employed.
8. Sample size will be calculated with an alpha of 0.05 and power of 80% to detect a change of 10%.  
We will have a minimum sample size of 392 subjects based on this calculation.

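### Aim 2 credits any fall in antibiotics to trainee confidence, but the antibiotic outcome is patient-level, supervisors get the device in the same weeks, and no analysis links confidence to prescribing

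*Combined protocol and SAP*

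**What the plan says.** Section 2 words Aim 2 as a chain: "To determine whether smartphone otoscope improves diagnostic confidence of trainees, thereby reducing frequency of antibiotic prescriptions for AOM". Section 5a gives the aim two primary outcomes, listed separately. Outcome A is "Rates of patients who receive antibiotics" and outcome B is "Levels of provider confidence in exam based on a standardized confidence measure". Outcome A mentions neither AOM nor the trainee, and outcome B speaks of providers where the aim speaks of trainees.

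On exposure, section 3a says: "During Cellscope weeks, trainees and supervisors will be given access to the Cellscope and asked to use this tool for their otoscopic exams". Allocation is by week within two-week blocks, "1 week where the Cellscope will be available and 1 week where only traditional otoscopy will be available", so both groups of clinicians change exposure together. Traditional otoscopes stay available in Cellscope weeks.

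On data capture, section 3a has "trainees and supervisors each fill out an index card survey to record the following outcomes", and the list includes "trainee confidence in exam, antibiotic prescription, need for conversion to traditional otoscopy, and whether a repeat exam was obtained". The card itself is not reproduced.

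Aim 3 makes the supervisor's repeat exam an outcome that may differ with the device. Section 5c lists general methods, among them t-tests, regression, repeated measures models and kappa. It names no mediation analysis and no model of prescribing on confidence.

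**The concern.** The aim asserts a mechanism: the device raises trainee confidence, and that confidence lowers prescribing. The measured endpoint lies at the far end of that chain, and a second clinician with the same device can also act on it.

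Two errors of interpretation become possible. If confidence rises and antibiotic receipt falls, the wording of Aim 2 invites the conclusion that one caused the other, although the fall could have come through supervisors. If receipt does not change, a real effect on trainees' own decisions could be hidden because supervisors settle the final decision in both arms.

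The assumed direction is also untested. A trainee who becomes surer that AOM is present may be more inclined to treat, so higher confidence need not mean fewer prescriptions.

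**Working it through.** **The plan's own figure.** The only figure nearby is the minimum of 392 subjects in section 5c (alpha 0.05, power 80%, change of 10%). It gives no baseline rate and names no outcome, and it does not say whether 392 is per arm or in total. With rounded normal quantiles, 1.96 + 0.84 = 2.80 and 2.80² = 7.84. The per-arm formula is

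n = [p1(1−p1) + p2(1−p2)] × 7.84 / 0.10².

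- Assumed rates of 10% and 20%: (0.09 + 0.16) × 7.84 / 0.01 = 196 per arm, or 392 in total.
- Maximum variance, 0.25 + 0.25: 0.50 × 7.84 / 0.01 = 392 per arm.

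The figure is reachable under either assumption and is not in dispute. The present point does not depend on it.

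**The chain against what is measured.**

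1. *Device to trainee confidence.* The card has a trainee confidence item and weeks are randomised, so this link can be estimated.
2. *Trainee confidence to trainee decision.* The plan does not define a record of the trainee's own decision, and no analysis relates confidence to prescribing.
3. *Trainee decision to what the patient receives.* Only the end result is a named outcome (2A), and it counts any antibiotic.
4. *A second route: device to supervisor to what the patient receives.* It is open in the same weeks as the trainee route, because supervisors are asked to use the device and allocation is by week.

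The difference in 2A between weeks is thus the total over both routes.

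**Illustration of why the total does not separate them.** Let s be the share of final antibiotic decisions set by the supervisor, dT the device's effect on trainee decisions and dS its effect on supervisor decisions. Then

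difference in receipt = (1−s) × dT + s × dS.

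All three quantities are assumed; the documents give none of them. In percentage points:

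| s | Trainee only (dT = −10, dS = 0) | Supervisor only (dT = 0, dS = −10) |
|---|---|---|
| 0 | −10 | 0 |
| 0.25 | −7.5 | −2.5 |
| 0.5 | −5 | −5 |
| 0.75 | −2.5 | −7.5 |
| 1 | 0 | −10 |

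At s = 0.5 the two mechanisms give the same result: 0.5 × (−10) + 0.5 × 0 = −5, and 0.5 × 0 + 0.5 × (−10) = −5. With s unknown, an observed difference does not determine dT. The table shows non-identifiability; it does not estimate a bias.

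**The case against.** The strongest reply is that the planned comparison already answers a useful question. Whether patients receive antibiotics is the result that matters to them, and giving the device to the whole team is a legitimate pragmatic choice. Antibiotics and confidence are already listed as separate outcomes. Each clinician completes a card with an antibiotic item, so a trainee-level entry may already exist. On this view the problem is one word in an objective and one undefined card item.

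Much of that stands. The effect of device availability on receipt can be estimated, and final receipt need not be replaced. What remains is that Aim 2 claims a mechanism which neither the outcomes nor the analyses test, and that nothing defines the trainee's entry as a decision made before supervisor input.

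A reader might infer more than the documents support:

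- *That every prescription follows supervisor review.* This is plausible from the supervisory role and the paired gradings, but the order of exam, review, card and prescription is not stated.
- *That supervisors have always used the device or watched the trainee's recording.* They are given access and asked to use it, but traditional otoscopes remain available, repeat exams are not said to be universal, and no text says supervisors view recordings.
- *That nothing in the design could isolate the trainee's decision.* The card's wording and timing are unknown, so this goes too far.
- *That a particular dilution applies.* No figure in the documents supports one.

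**Conclusion.** The concern holds as a problem of attribution. Following the plan as written can show whether device availability changes antibiotic receipt and whether it changes confidence. It cannot show that the first follows from the second. The antibiotic outcome is also broader than the aim, since it is not limited to AOM.

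The conclusion rests on stated text: the wording of Aim 2 and of outcome 2A, device access for supervisors in the same weeks, the undefined antibiotic item, and the absence of any analysis linking confidence to prescribing. It does not require that supervisors review every case before prescribing, only that they can influence the result. The size of any masking or misattribution is unknown; the 0 to 10 point range in the table follows from assumed inputs.

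The randomised comparison survives, so this does not undermine the trial as a whole. It should be settled before data collection, because a trainee's plan before supervision cannot be recovered reliably afterwards.

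**What to change.** 1. On the existing trainee card, in both arms, define an item completed before any supervisor input: *My plan: antibiotic for AOM, yes/no*. Compare it between Cellscope and traditional weeks as the trainee-decision outcome, beside trainee confidence. If the present antibiotic item was meant to serve this purpose, state whose decision it is and when it is recorded.
2. Keep final antibiotic receipt as the whole-team outcome and restrict it to antibiotics given for AOM, to match the aim. Apply the restriction to the indication and keep all enrolled patients in the denominator, since the device may itself change who is diagnosed with AOM.
3. Delete *thereby* from Aim 2, and report trainee confidence and antibiotic prescribing as separate effects of the allocated week. Use the word trainee in outcome 2B, as the aim and the card do.

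The cost is one card item, small edits to Aim 2 and its outcomes, and loss of the causal wording. Asking trainees to commit to a plan before presenting may slightly affect their decisions, but the request is the same in both arms. The new item separates the trainee's decision from the team's. It still would not prove that confidence is the mediator, which is why the wording must change as well.

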## 3. Study Procedures

### a. Study design, including the sequence and timing of study procedures

This is a prospective, randomized, unblinded, controlled study in the Harriet Lane Clinic (HLC), the Johns Hopkins Children's Center pediatric primary care resident teaching practice and the Johns Hopkins Children's Center Pediatric Emergency Department (Peds ED). The HLC has clinics for acute care (e.g., sick visits) and continuity (e.g., well child and follow-up visits). We will purchase Cellsopes, iPhones, phone cases, and locking storage systems for each setting. There will be no direct collaboration between the study investigators and Cellscope related to this study. We will evaluate the above aims by block-randomizing in 2-week blocks: 1 week where the Cellscope will be available and 1 week where only traditional otoscopy will be available. Because residents rotate through the HLC and Peds ED in 2 and 4-week rotations, this will allow for the inclusion of the same trainees in each arm to act as their own control and ensure there is no use of the Cellscope during the traditional-only weeks. During Cellscope weeks, the traditional direct otoscopes will be available based on trainee/supervisor preference. During the traditional weeks, the Cellscope will not be available, thus the standard of care will not be changed during our study. iPhones will be secured with 6-digit numeric passcodes, in compliance with JHMI security standards. Recordings/images of external and middle ear structures will be obtained in a HIPAA compliant manner without collecting any PHI.

During Cellscope weeks, trainees and supervisors will be given access to the Cellscope and asked to use this tool for their otoscopic exams (research procedure). They will have full discretion of when an otoscopic examination is indicated, based on their existing practice and standard of care. We will then ask that the

trainees and supervisors each fill out an index card survey to record the following outcomes: agreement between trainee and supervisor using the OMgrade scale (validated otitis media diagnostic tool), trainee confidence in exam, antibiotic prescription, need for conversion to traditional otoscopy, and whether a repeat exam was obtained. During the traditional weeks, the Cellsopes will be unavailable, locked in an enclosure, and traditional otoscopy (routine care) will be the only method available. The same index card survey will be completed by the trainees and supervisors. There will be no change to patient restraint, as described above.

b. Study duration and number of study visits required of research participants.

The study will last for between 9-12 months depending on the number of patients enrolled. Only one study visit is required per research participant. The same patient will be able to be included in the study multiple times if they present to the HLC or Peds ED on multiple occasions.

c. Blinding, including justification for blinding or not blinding the trial, if applicable.

This study will be unblinded. It is not possible to perform this study in a blinded manner given the obvious difference in the handheld hardware.

d. Justification of why participants will not receive routine care or will have current therapy stopped.

Standard of care is traditional direct otoscopy, as described above. We are using an equivalent method of otoscopy that allows the identical visualization of the external and middle ear structures. It will also be explicitly stated to providers that they can revert to traditional otoscopy if they feel that the Cellscope is not able to identify the needed structures.

e. Justification for inclusion of a placebo or non-treatment group.

N/A

f. Definition of treatment failure or participant removal criteria.

If any provider feels that the Cellscope is not able to appropriately identify the needed ear structures, that will be considered a failure of the Cellscope, and that provider will be able to immediately revert to a traditional otoscope. Furthermore, patients and guardians may opt for providers to use the traditional otoscope at any time. This will be tracked.

g. Description of what happens to participants receiving therapy when study ends or if a participant's participation in the study ends prematurely.

Resumption of traditional care, without any harm to the patient.

h. Informed Consent

If patients are interested in participating the trainees or supervisors will obtain informed verbal consent from the parent or legal guardian of the patient prior to examining the child. Explaining the study, obtaining consent, answering questions, and assessing parent and patient understanding is expected to take under 5 minutes, which is typical for a similar conversation clinical setting. A copy of the IRB protocol will be provided upon request. A waiver of written consent is requested because the consent document is the only record linking the subject and the research. The research presents no more than minimal risk of harm to subjects and involves no procedures for which written consent is normally required outside of the research context.

i. Provider Training

Providers will be trained on setting up the Cellscope: attaching the case to the iPhone, attaching the Cellscope to the case, turning on the iPhone and unlocking it. They will also be trained on how to use the Cellscope application to record non-PHI containing images/videos. This training will be done by members of the study team who are proficient in using the device and app. This will occur in whatever clinical setting, in which they are assigned (Pediatric Emergency Room, Harriet Lane Acute Clinic, Harriet Lane Continuity Clinic). This will take place prior to them using the device on any patients for the purposes of this study or any other indication.

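### How week order is drawn within each 2-week block is not stated and the matched tests carry no week term, so chance order imbalance can let a week-to-week gain shift the Cellscope contrast by a modest amount

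*Combined protocol and SAP*

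**What the plan says.** Section 3a sets the allocation as "block-randomizing in 2-week blocks: 1 week where the Cellscope will be available and 1 week where only traditional otoscopy will be available". Since every block holds one week of each kind, the only thing left to randomise is which comes first. The section does not say how that is decided, whether the two orders are to be equal in number, or whether the clinic and emergency department settings share one sequence.

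The reason given for the weekly switch is "Because residents rotate through the HLC and Peds ED in 2 and 4-week rotations", so that the same trainees contribute to both arms. Whether rotations start at block boundaries is not stated.

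On duration, section 3b says "The study will last for between 9-12 months depending on the number of patients enrolled".

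Section 5c lists methods in general terms. Item 4, the one that matches the own-control design, is "Estimation and testing of within-person changes by matched t-test or Wilcoxon signed-rank test". Items 5 and 6 add "Multiple linear regression, logistic regression, or Cox proportional hazards regression" and "Repeated measures models (usually requires the help of a statistician"). No week, order or calendar term is named in any of them. The sample-size item reads "Sample size will be calculated with an alpha of 0.05 and power of 80% to detect a change of 10" per cent, followed by "We will have a minimum sample size of 392 subjects based on this calculation".

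**The concern.** Trainees may do better in the second week of a block than in the first whichever instrument is in the room, through practice at otoscopy and familiarity with the survey card and the OMgrade scale. Agreement with the supervisor, confidence and repeat examinations are all open to such a change. This is a period effect, distinct from anything carried over from using the Cellscope.

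A trainee who spends two weeks in a setting sees only one order, so that trainee's matched difference contains the device effect plus or minus the weekly gain. Two things follow. If one order turns up more often than the other, part of the gain enters the arm contrast. Even if the orders come out equal, the gain remains as extra spread in the matched differences. Everyone in a setting shares that setting's sequence, so enrolling more patients per week does not reduce the order imbalance. Only more blocks or more independent sequences do.

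**Working it through.** **The plan's own figure.** With two-sided alpha 0.05, 80% power, and 45% versus 55% (a baseline assumed here, since none is given), the pooled formula gives n = [1.960 × √0.5 + 0.842 × √0.495]² / 0.10² ≈ 391.3, so 392 per arm. Read as a total, 392 is close only to rates such as 10% versus 20% (197 to 199 per arm, 394 to 398 in total). The documents do not say which is meant. The point below does not depend on it; both readings are used only to set a scale.

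**Inputs.**
- Blocks: 9 to 12 months (section 3b) is about 39 to 52 weeks, so 19 to 26 complete 2-week blocks per sequence.
- Order: an independent fair coin per block (assumption; the method is not stated).
- Weekly gain d: 2, 5 or 10 percentage points (assumption; no learning rate is given).
- Equal patient numbers per week, and rotations aligned with blocks (assumptions).

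**Formula.** A block with Cellscope second estimates effect + d, and a block with Cellscope first estimates effect − d. Averaged over B blocks:

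shift = d × (Cellscope-second blocks − Cellscope-first blocks) / B

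The bracket divided by B is the order imbalance. Its mean is 0 and its RMS is 1/√B.

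| | B = 19 | B = 26 |
|---|---|---|
| RMS imbalance | 0.229 | 0.196 |
| 95% bound on absolute imbalance | 0.474 | 0.385 |
| P(absolute imbalance ≥ 0.2) | 0.36 | 0.33 |
| RMS shift, d = 2 (95% bound) | 0.46 (0.95) | 0.39 (0.77) |
| RMS shift, d = 5 (95% bound) | 1.15 (2.37) | 0.98 (1.92) |
| RMS shift, d = 10 (95% bound) | 2.29 (4.74) | 1.96 (3.85) |

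**Separate sequences.** If three settings are randomised separately there are 57 to 78 blocks. The RMS imbalance is then 0.133 to 0.113, and for d = 5 the RMS shift is 0.66 to 0.57 points.

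**Effect on type I error.** This uses a normal approximation for two proportions near 50%, ignoring clustering. The standard error is √(2 × 0.25/n): 5.05 points at 196 per arm and 3.57 at 392 per arm. Averaged over the possible imbalances in one sequence:

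| d | 196 per arm | 392 per arm |
|---|---|---|
| 2 | 5.1% | 5.1–5.2% |
| 5 | 5.4–5.6% | 5.9–6.2% |
| 10 | 6.8–7.4% | 8.6–9.9% |

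**Variance of matched differences.** For 2-week trainees with the two orders equally frequent, the ±d term adds d² to the variance: 4, 25 or 100 squared points. The documents give no standard deviation for these differences, so the relative widening of the interval cannot be stated.

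**With order balance.** For an even number of blocks and equal weekly numbers, the shift from a constant additive gain is 0. For 19 blocks the smallest possible imbalance is 1/19, leaving 0.05 × d, or 0.26 points at d = 5.

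**The case against.** The strongest reply is that this is small and partly conjectural. A reader might infer that the plan leaves order unbalanced. The text does not show that: it is silent on how order is drawn, and the list may be balanced in practice. A reader might also infer a systematic bias from learning. Under random order there is none, since the shift averages zero and is a matter of chance imbalance and added noise. At an assumed 5-point weekly gain it is about 1 point. It becomes material only as the gain approaches 10 points per week, and no document supports a particular value.

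A third tempting reading is that a mirrored order over four weeks would cancel the trend outright. It does so for a straight-line gain only. Suppose the levels over four weeks were 0, 5, 8 and 9 (illustrative). Cellscope-traditional-traditional-Cellscope gives means of 4.5 and 6.5, still a 2-point gap, against 4 and 7, a 3-point gap, under strict alternation.

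Two more points stand in part. Section 5c also lists regression and repeated-measures models, so a week term is not excluded; it is simply not specified, like every other covariate. And the rotation lengths are given for residents only. Where rotations start mid-block, week in block is not week of rotation, so the shift is smaller and a week-in-block term would not measure learning.

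These objections limit the size and the wording. They do not answer the request itself: an own-control comparison over two periods should state how order is assigned and should carry a period term.

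**Conclusion.** The point holds in a limited form. The protocol specifies neither the method of drawing week order nor any balance of orders, and the matched tests it lists for within-person change have no week term. If order is drawn independently per block in one sequence, the contrast is unbiased on average, with an RMS shift of about 0.4–0.5, 1.0–1.1 or 2.0–2.3 points for assumed weekly gains of 2, 5 or 10 points. The shift is smaller if the settings are randomised separately. The comparison with the planned 10% change assumes that change is absolute, which the plan does not say. The sizes apply to percentage outcomes such as raw agreement or the repeat-examination rate and do not transfer directly to kappa.

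The documents do not support calling the design biased or its order unbalanced. This is a low-cost gain in precision and protection against an unlucky sequence.

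**What to change.** 1. State in section 3a how week order is generated and whether the settings share a sequence. Constrain the list so that Cellscope-first and traditional-first blocks are equal in number, for example by taking blocks in pairs with one of each order and randomising which comes first.
2. In section 5c, replace the unadjusted matched tests for arm comparisons with a within-trainee model that includes arm and a period term: week in block, or week of rotation where rotations do not start with a block.

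Together these remove a constant additive week effect, and the model term does so even when weekly patient numbers differ. Order balance alone is exact only with complete sets and similar weekly numbers; since duration depends on enrolment, the trial may stop part-way through a pair. Neither step removes carryover of skill from a Cellscope week into a following traditional week, or learning that differs by arm.

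The cost is a revised list and one extra model term. Pairing also makes the second block's order predictable and halves the number of random draws. In an open trial where the second week of each block is already known, that is a slight loss, though not nil, because clinicians decide when otoscopy is indicated.
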